#### 4.4. Main outcomes and measures

#### 4.4.1. Outcomes

The primary outcome will be measured only among patients who have common potential drugdrug interactions (DDIs) based on a pre-specified list of medications. The outcome will be whether the patient received counseling for any valid potential DDI. For patients with more than one DDI, the outcome will counted as present if they received counseling for any of their potential DDIs.

Secondary outcomes will be:

- a. % of all patients who were prescribed Paxlovid (based on orders)
- b. Hours from the e-visit request to the prescription order being placed, among patients who were prescribed Paxlovid
- c. Clinician minutes per message handled. This will be analyzed using EPIC access log data. We will link each e-visit for Paxlovid with the relevant secure messages and/or

telephone encounters, including follow-ups that occurred before the initial request was resolved. Clinicians include pharmacists and physicians.

- d. Estimated personnel cost per Paxlovid message handled. The estimated cost per message handled will be calculated by multiplying the number of minutes spent per message by the standard wage rate for a pharmacist or AFM in Northern California.
- e. Patient satisfaction with care

Exploratory outcomes will be:

- a. Number of Paxlovid e-visits handled by the regional pharmacy team, per week
- b. % of messages fully handled by the initial clinician (pharmacist or AFM) (based on review of visits)
- c. % of cases handled by pharmacists that required a physician consultation (based on review of visits)
- d. Pharmacist satisfaction with the process of care [Note: Deleted "AFM satisfaction" as a measure because there was not a logical group of AFMs to survey, nor logical questions to ask them.]
- e. % of all patients who obtained Paxlovid (based on fills)
- f. Days from request to receipt of medication among patients prescribed Paxlovid
- g. % of patients with common potential DDIs who were prescribed Paxlovid
- h. If feasible based on ICD-9 codes: Incidence of drug reactions due to Paxlovid DDIs within 10 days after a Paxlovid prescription

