The pharmacist and physician surveys have been designed to require no more than 3 to 5 minutes to complete. These surveys will be fielded via Outlook email using a Teams form, as well as on paper via interoffice mail. A small gift to thank pharmacists and physicians for considering participation will be included in the mailing. Responses will be treated as confidential and data will be aggregated, with no individual identifiers associated with data presented in reports.

Data collected from both pharmacists AFMs and will include:

- a. Satisfaction with the process of care (on a 5-point scale)
- b. Suggestions for improving the care process (open-ended)

4.6. Statistical analysis plan.

During the survey and visit review components of this study, it became clear that more patients than projected had received pharmacist care. A preliminary analysis conducted on 12/18/2024, prior to evaluating any outcomes, found that the facility assigned to each e-visit usually did \*not\* match the home facility of the patient who initiated the e-visit. This was most likely due to an operational workflow (which is still being elucidated) that was unanticipated at the time this study was designed and facilities were assigned at random to the Pharmacist Care vs. Physician Care groups. Due to the fact that the patient's "home" facility became imbalanced, we will include this as a covariate in the primary analysis (see below).

The primary analysis will group each patient based on which type of clinician (pharmacist or physician) first accessed the eVisit. This is similar to a per-protocol analysis. A patient whose eVisit was first accessed by a pharmacist will be counted in the pharmacist group, even if the eVisit was referred to a physician. A patient whose eVisit was first accessed by a physician will be included in the physician group, even if the eVisit was referred to a physician group, even if the eVisit was referred to a physician group, even if the eVisit was referred to a pharmacist. We select this approach as the primary analysis because it best reflects what patients experience in real-life care delivery, which this study is intended to evaluate.

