A secondary analysis will treat each patient as part of the group to which they were assigned based on the facility listed on the e-visit worklist (intention-to-treat). However, this approach may be worse at reflecting the actual patient experience because dozens of pharmacists and physicians were involved in executing the randomization assignments. It is possible that some patients will have received a different mode of care from the group to which they were assigned.

The primary outcome is binary, i.e., whether or not a patient received counseling for a DDI. This will be compared between study groups using mixed effects logistic regression providing point and interval estimates of outcome odds ratios associated with study group. This analysis technique accounts for the within-facility correlation among patients to obtain valid estimates of treatment effects and associated standard errors. The pre-specified set of covariates for inclusion in regression models include: study group and covariates used in the randomization procedure (i.e. patient socioeconomic status (using the Neighborhood Deprivation Index), patient race/ethnicity, and service area level COVID-19 incidence). Study group and other covariates will be treated as fixed effects and the patient's home facility and e-visit facility will be handled as random effects.

In addition, exploratory/sensitivity analyses will examine the impact of including additional covariates in our estimation of treatment effect, with focus on variables with chance imbalance in distributions by treatment group, as determined in preliminary analyses. Analyses resulting in an appreciable change in the estimate of treatment differences or increased precision of the treatment effect will be noted.

For the secondary outcomes, we will compare the estimated cost per Paxlovid message, the minutes spent per message, and the hours from e-visit to prescription order between the Pharmacist Care and AFM Pool Care groups using linear mixed regression models, providing point and interval estimates of between-group differences in mean outcomes. If cost or minutes have a skewed distribution, log transformation will be used. Analyses of other secondary outcomes with that are continuous will be similar. The approach to inclusion of covariates and sensitivity/exploratory analyses is as described for Aim 1.

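### Hours to prescription run from the request, but the main analysis fixes the group later, at first access, so waiting on one team's worklist can be credited to the other team

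*Combined protocol and SAP*

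**What the plan says.** Section 4.4.1 defines secondary outcome b as "Hours from the e-visit request to the prescription order being placed, among patients who were prescribed Paxlovid". The abstract lists faster prescribing among the hypotheses to be tested.

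Section 4.6 sets the grouping: "The primary analysis will group each patient based on which type of clinician (pharmacist or physician) first accessed the eVisit". Later hand-offs do not change it. A patient whose e-visit a pharmacist opened first "will be counted in the pharmacist group, even if the eVisit was referred to a physician", and the mirror rule applies to physicians. The section gives this grouping for the primary analysis in general and no different one for hours, so it appears to govern outcome b, although this is not said outcome by outcome. The plan then compares "the hours from e-visit to prescription order between the Pharmacist Care and AFM Pool Care groups using linear mixed regression models".

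A secondary analysis places each patient in the group "to which they were assigned based on the facility listed on the e-visit worklist (intention-to-treat").

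On departures from assignment, section 4.6 reports that "it became clear that more patients than projected had received pharmacist care". It attributes the mismatch between home facility and e-visit facility to a cause described as "due to an operational workflow (which is still being elucidated) that was unanticipated", and adds: "It is possible that some patients will have received a different mode of care from the group to which they were assigned". It gives no crossover rate, no queue times and no route by which an e-visit would pass from one team to the other.

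**The concern.** First access happens after the request, so group membership is decided partway through the interval being measured. All the time before opening goes to whichever team opens the e-visit. If the e-visit had been waiting on the other team's worklist, that wait is credited to the wrong team, and the team that left it unopened loses a slow case from its own mean. After a referral the same happens in the other direction: the second team's delay stays with the first opener.

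Nothing planned removes this. The fixed-effect covariates in section 4.6 (deprivation index, race/ethnicity, service-area COVID-19 incidence) do not measure time in a queue. The e-visit facility random effect does not help either. Within a facility assigned to the physician pool, a pharmacist-versus-physician contrast is a contrast of crossed-over with non-crossed-over e-visits, which is where the distortion sits.

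At stake is the lead estimate for a timeliness hypothesis named in the abstract.

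**Working it through.** **1. The plan's nearest design figure.** No detectable difference is stated for hours. For cost (Aim 2), section 4.8 states 0.20 SD at 80% power. Inputs from section 4.8: 1,560 e-visits, 17 clusters of 92, ICC 0.01; alpha 0.05 two-sided from section 4.6.
- Design effect = 1 + (92 − 1) × 0.01 = 1.91.
- Effective size per arm = 780 / 1.91 = 408.
- Detectable difference = (1.960 + 0.842) × √(2/408) = 0.196 SD; power at 0.20 SD is 81.5%.

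The stated 0.20 SD reproduces. It serves below only as a yardstick, since hours are measured in prescribed patients alone.

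**2. Where the wait goes.**

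| Path of the e-visit | Wait before opening | Credited to | Misattributed? |
|---|---|---|---|
| Worklist team opens it | that team's | that team | no |
| Routed at entry to the other team's worklist, opened there | the other team's | the other team | no |
| Waits on one team's worklist, first opened by the other | first team's | the opener | yes |
| Opened by one team, then referred | opener's, then the second team's delay | the opener throughout | second part, yes |

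**3. Size under assumed inputs.** Suppose (assumption) equal teams, equal-sized assigned groups, exponential queue time with mean 2 h and exponential handling time with mean 1 h. The SD of the total is √(2² + 1²) = 2.24 h. A share c of physician-assigned e-visits is first opened by pharmacists. Each e-visit's total time is left unchanged, so only the group label moves and the true difference is 0.

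If the crossing e-visits exceed the average wait by w hours on average:
- the pharmacist mean rises by c·w/(1 + c);
- the physician mean falls by c·w/(1 − c);
- the spurious difference (pharmacist minus physician) is 2·c·w/(1 − c²).

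Random crossover with equal queues gives w = 0, so the difference is 0. If the longest waiters cross, w = 2·ln(1/c):

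| c | w (h) | Spurious difference (h) | In SD |
|---|---|---|---|
| 5% | 5.99 | 2 × 0.05 × 5.99 / 0.9975 = 0.60 | 0.27 |
| 10% | 4.61 | 2 × 0.10 × 4.61 / 0.99 = 0.93 | 0.42 |
| 20% | 3.22 | 2 × 0.20 × 3.22 / 0.96 = 1.34 | 0.60 |
| 40% | 1.83 | 2 × 0.40 × 1.83 / 0.84 = 1.74 | 0.78 |

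A simulation of 400,000 e-visits agreed to within 0.01 h. Grouping by assigned worklist gave 0.0 h at every c.

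**4. A truly slower physician queue (assumption: mean 4 h against 2 h, true difference −2.0 h), c = 20%.**
- Random crossover: pharmacist mean (3 + 0.2 × 5)/1.2 = 3.33 h, physician mean 5 h, difference −1.67 h.
- Longest waiters cross: their mean queue is 4 + 4·ln 5 = 10.44 h, so their mean total is 11.44 h. Pharmacist mean (3 + 0.2 × 11.44)/1.2 = 4.41 h; physician mean (5 − 0.2 × 11.44)/0.8 = 3.39 h; difference +1.02 h, the wrong sign.
- Worklist grouping gives −2.0 h in both cases.

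**The case against.** The strongest reply is that the documents never describe an e-visit waiting with one team and being opened by the other. The only mismatch they report is between home facility and e-visit facility, which fits routing at entry, and they call other departures merely possible. This stands. A reader might infer that every crossover misattributes time; the documents do not support that, because an e-visit placed at entry on the other team's worklist never waited with the first team.

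Second, the plan already contains an analysis by worklist facility, in which group and clock are both set at or near the request. This also stands: no analysis is missing. What remains is which analysis leads, and section 4.6 gives the lead to first access.

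Third, misattribution need not bias the comparison. It is zero under random crossover with equal queues, and the larger figures above rest on the extreme case in which exactly the longest waiters cross.

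Fourth, some illustrations overstate the error. Suppose both queues have exponential waits of mean 3 h, and e-visits unopened by team A at 4 h are opened by team B a mean 0.5 h later. First-opener means are 1.57 h and 3.31 h, a gap of 1.7 h. A reader might call all of it false. But A-assigned patients then really do wait less: 0.736 × 1.57 + 0.264 × 4.5 = 2.34 h against 3.0 h, so 0.66 h remains under assigned grouping. For this reason the working above keeps totals unchanged.

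Finally, request to order is the interval patients experience, and its definition is sound. The fault lies in pairing it with a grouping fixed later.

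**Conclusion.** The structural point holds on the plan's own wording: the clock for outcome b starts before the event that defines the main analysis group, and nothing in section 4.6 corrects for it. It bites only where the first opener differs from the worklist group, or after a referral.

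The size cannot be computed from the documents. Under the stated assumptions it runs from zero to 0.27–0.78 SD for 5–40% crossover of the longest waiters; the upper part of that range exceeds the 0.20 SD the plan gives for cost.

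The direction is also unknown. A reader might infer that the grouping flatters pharmacists. The documents do not support that: if the reported excess of pharmacist care reflects long-waiting physician-pool e-visits opened by pharmacists, pharmacists would look slower, against the trial's hypothesis.

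The outcome is secondary, but the hypothesis is named in the abstract and the repair is cheap, so the change is worth making.

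**What to change.** In section 4.6, for hours to prescription:
- Make the planned worklist-facility (intention-to-treat) comparison of request-to-order hours the one that judges the abstract's timeliness hypothesis.
- Tabulate worklist group by first opener, so that the crossover rate is visible.
- Under first-access grouping, split the interval into request to first access and first access to order. Attribute only the second part to the opener's group, and label any request-to-order contrast there as descriptive. State that delay after a referral remains in the second part.

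The cost is SAP wording. First access must already be identified to form the groups, and the worklist analysis is already planned. The downsides are one more interval to report, and a worklist comparison that is diluted where care departed from assignment. That comparison also relies on a facility field shaped by a workflow not yet understood, so the plan should state when the field is set.

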## 1. Specific Aims and Hypotheses

Enhancing message management and virtual urgent care options for patients are among TPMG and KFH's top priorities. As team-based inbox management is further developed, evaluating its clinical effectiveness and outcomes in terms of patient care experience and costs will provide valuable information for operational planning. In addition, sharing what we learn with other health care systems through talks and publications will help highlight TPMG's reputation as a group that innovates to support clinicians while increasing patient access through virtual care.

This study will compare the clinical outcomes and costs of two alternative modes of management of patient requests for Paxlovid sent via e-visits: management by a regional team of pharmacists, vs. management by medical center-based pools of adult and family medicine physicians (AFMs) doing desktop medicine. We will conduct a cluster randomized trial in 17 facilities in Kaiser Permanente Northern California to compare Pharmacist Care with AFM Pool Care for patients making Paxlovid e-visits with regard to:

Aim 1. Quality of care

Example hypothesis: Patients with common potential DDIs will be more likely to receive relevant counseling in the Pharmacist Care group than the AFM Pool Care group.

Aim 2. Clinician time and costs

Example hypothesis: Pharmacist Care will have lower costs of clinician time per Paxlovid e-visit managed than AFM Pool Care.

Aim 3. Exploratory outcomes

Example hypothesis: Patients in the Pharmacist Care will report comparable satisfaction with the process compared with the AFM Pool Care group.

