Patient satisfaction and other care experience scores will be compared between the study groups using linear mixed effects regression with log transformation if needed for skewed data, with analyses paralleling that described for the other secondary outcomes.

For all aims, secondary analyses will assess variation in the estimates of treatment effect by age, race/ethnicity/language group, and comorbidity score group (high, medium, low) via stratification by level of the potential effect modifier. These stratified analyses will inform the fitting of regression models with appropriate cross-product terms between the potential effect modifier and study group indicator variable, allowing for a more formal assessment of heterogeneity in treatment effect.

A service area or facility may drop out before completion of the study if they were assigned to AFM Pool Care but add local pharmacist management, thus diverging from their assigned group. Paxlovid e-visits from such a service area or facility will be censored as of the dropout date (the date that local pharmacist management began).

Tests of significance will be two-tailed with an alpha of .05. No Bonferroni or other formal correction for multiple comparisons will be used, but results will be interpreted with the multiple testing issue in mind.

4.8. Sample size and power. To estimate the available sample, we extrapolated from April 2023. This was a month when COVID-19 incidence was low to medium; 4900 e-visits for Paxlovid were made across the 15 KPNC service areas. Based on this, an average of 1089 e-visits occur per week during low to medium COVID-19 incidence periods. However, e-visits that need to be answered on weekend days will not be eligible for pharmacist management; all of these will be excluded from the study. If 5 out of 7 e-visits occur on weekdays, an estimated 778 e-visits occur on weekdays during times of low to medium COVID-19 incidence.

This study will include 17 facilities that serve 872,200 adult members, or 25% of the 3.55 million adult members in the region. Each week, the estimated number of e-visits eligible for study is 25% of 778, or 195. Assuming an 8-week evaluation period, the estimated sample size is 1,560, or 92 patients in each of the 17 clusters.

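### Aim 2 cost is clinician minutes priced at one wage per clinician type, with no analysis that varies the wage, so a lower-cost result is conditional on that input

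*Combined protocol and SAP*

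**What the plan says.** Secondary outcome c in section 4.4.1 is clinician minutes per message, taken from access logs; "Clinicians include pharmacists and physicians". Outcome d is cost, found by "multiplying the number of minutes spent per message by the standard wage rate for a pharmacist or AFM in Northern California". Neither rate is given, nor a source or year.

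Aim 2 (section 1) offers the hypothesis that "Pharmacist Care will have lower costs of clinician time per Paxlovid e-visit managed than AFM Pool Care", and the Abstract repeats the expectation of lower cost.

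Section 4.6 analyses cost alongside minutes and hours to prescription, "using linear mixed regression models, providing point and interval estimates of between-group differences in mean outcomes". It adds: "If cost or minutes have a skewed distribution, log transformation will be used". The planned "exploratory/sensitivity analyses will examine the impact of including additional covariates in our estimation of treatment effect"; none varies the wage. On testing: "Tests of significance will be two-tailed with an alpha of .05".

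Section 4.6 also reports that "it became clear that more patients than projected had received pharmacist care", and forms the primary analysis groups by the type of clinician who first opened the e-visit, whether or not it was later referred. The realised split is not given.

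**The concern.** Outcome d is built from outcome c and an outside price. For an e-visit handled by one clinician type, log cost is log minutes plus a constant. The cost test then asks only whether the pharmacist:AFM minutes ratio is below the AFM:pharmacist wage ratio. One side of that comparison comes from trial data with a standard error. The other is a fixed figure that the plan neither states nor varies.

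A second issue arises if cost stays on its raw scale. Unequal wages stretch the two groups' costs by different factors, so similar minutes SDs become unequal cost SDs. A linear mixed model with one residual variance ignores this, and group sizes defined by first access are not fixed by the randomization.

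The result matters because lower cost is a stated hypothesis, and the Projected Impact section says the findings will inform how pharmacist effort is deployed.

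**Working it through.** **Inputs from the plan.** Section 4.8: 1,560 e-visits, 17 clusters of about 92, ICC .01, two-sided alpha .05, and a detectable Aim 2 effect of 0.20 SD at 80% power. Equal groups would be 1,560/2 = 780.

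**Assumptions.** The plan gives no wages, mean minutes, SDs or realised split. I assume a CV of minutes of 0.6 to 1.0, AFM:pharmacist wage ratios W of 1.25 to 3, and pharmacist shares p of 33% to 70%.

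**The plan's own figure.** Design effect = 1 + (92 − 1) × 0.01 = 1.91. Effective size per group = 780/1.91 = 408.4. Detectable effect = (1.960 + 0.842) × √(2/408.4) = 0.196 SD, which rounds to the stated 0.20.

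**Wage dependence.** For single-clinician e-visits, log cost ratio = log(minutes ratio) − log W, with SE ≈ CV × √(2/408.4) = CV × 0.0700. The wage ratio must change by a factor of exp(2 × 1.96 × SE) to move the result from just-significant excess to just-significant saving:

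| CV | SE | Factor |
|---|---|---|
| 0.6 | 0.042 | 1.18 |
| 0.8 | 0.056 | 1.25 |
| 1.0 | 0.070 | 1.32 |

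Example at CV 0.8 with pharmacists taking 1.5 times the minutes: exp(1.96 × 0.056) = 1.116. There is significant excess below W = 1.5/1.116 = 1.34 and significant saving above W = 1.5 × 1.116 = 1.67.

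Pharmacist:AFM cost ratio (minutes ratio divided by W) and verdict at CV 0.8:

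| Minutes ratio | W = 1.25 | 1.5 | 1.75 | 2.0 | 3.0 |
|---|---|---|---|---|---|
| 1.0 | 0.80 lower | 0.67 lower | 0.57 lower | 0.50 lower | 0.33 lower |
| 1.25 | 1.00 n.s. | 0.83 lower | 0.71 lower | 0.62 lower | 0.42 lower |
| 1.5 | 1.20 higher | 1.00 n.s. | 0.86 lower | 0.75 lower | 0.50 lower |
| 2.0 | 1.60 higher | 1.33 higher | 1.14 higher | 1.00 n.s. | 0.67 lower |

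At a minutes ratio of 1.0 nothing flips.

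**Untransformed cost.** With equal minutes SDs, the AFM cost SD is W times the pharmacist one. Up to a common factor:

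- true variance of the difference = 1/p + W²/(1 − p)
- common-variance version = [p + (1 − p)W²] × [1/p + 1/(1 − p)]

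For W = 2 and p = 0.7: true 14.76, common 9.05, SE ratio √(9.05/14.76) = 0.783, coverage 2Φ(1.96 × 0.783) − 1 = 88%.

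| Pharmacist share | W = 1.5 | W = 2.0 |
|---|---|---|
| 33% | 97.5% | 98% |
| 50% | 95% | 95% |
| 60% | 93% | 92% |
| 70% | 91% | 88% |

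Simulations with facility effects at shares of 33%, 50%, 67% and 75% show the same pattern. At W = 2, coverage was 97.4% at a 33% share, 93.7% at 50% and 88.5% at 67%.

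**Referred e-visits.** Sections 4.4.1 and 4.5 count both clinician types' minutes, and section 4.6 keeps a referred e-visit in its first-access group. Cost is then not total minutes times a group constant. With mean pharmacist minutes P and physician minutes A in each group, break-even W = (P in pharmacist group − P in AFM group) / (A in AFM group − A in pharmacist group). Illustration with assumed figures: 13.5 pharmacist and 1.5 physician minutes in the pharmacist group, against 10 physician minutes in the AFM group. Break-even is 13.5/(10 − 1.5) = 1.59, whereas the ratio of total minutes is 15/10 = 1.5.

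**The case against.** A fixed price is a legitimate way to value time, and the interval is valid conditional on it. Cost is secondary and labelled as estimated. Minutes are analysed separately without any wage, so the dependence is visible to a careful reader. The Abstract expects pharmacists to use less clinician time, in which case nothing flips. All of this stands. It makes the wage question conditional but does not remove it: the plan also expects pharmacists to counsel more often on drug interactions, which may take time, and the hypothesis claims lower cost without reference to a wage.

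A reader might infer that the raw-scale intervals are too narrow in general. The documents do not support that. The direction depends on the split. Section 4.6 makes a pharmacist majority plausible but does not report one, and it names no residual structure, so the common variance is itself an assumption. The log rule would also probably apply: minutes cannot be negative, and at CV 0.8 a normal distribution would put Φ(−1.25) = 11% of values below zero, so such data would be right-skewed. Logging removes the wage-driven variance difference for single-clinician e-visits, though not the wage dependence.

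The design effect of 1.91 assumes whole facilities in one group, whereas first access can vary within a facility. With no design effect, the SE is CV × √(2/780) = CV × 0.0506, and the flip factors become exp(3.92 × 0.0506 × CV) = 1.13, 1.17 and 1.22 for CV 0.6, 0.8 and 1.0. Smaller wage changes would then suffice, so this objection alters the size and not the conclusion.

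**Conclusion.** The point holds in conditional form. The Aim 2 cost result depends on an unstated wage input, and no planned analysis shows how much. Where pharmacists take longer and the minutes ratio is near the wage ratio, a change of about 18% to 32% in the wage ratio reverses a significant result, given CV 0.6 to 1.0, 780 per group and ICC .01. It would be wrong to infer that the wage alone decides Aim 2 whatever the data show: if pharmacists take no longer and are paid less, the verdict is stable.

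The interval problem is narrower still. It needs untransformed cost, a common residual variance, similar minutes SDs and a pharmacist majority. Coverage is then about 88% to 93% at shares of 60% to 70% and wage ratios of 1.5 to 2. It is correct at equal sizes and conservative if the AFM group is larger. Because the plan's own power figure reproduces, nothing here questions the sample size. This should be changed, as a matter of analysis and reporting for a secondary outcome.

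**What to change.** Amend section 4.4.1, outcome d, and section 4.6 as follows:

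- Compute cost per e-visit by pricing pharmacist minutes and physician minutes separately, each at its own wage, including referred e-visits.
- State both wages and their source.
- Use cluster-robust or group-specific variances whenever cost is analysed untransformed.
- Report the cost difference with its 95% CI over a prespecified wage range.
- Report the break-even AFM:pharmacist wage ratio with its CI, calculated from mean pharmacist and mean physician minutes in each group and not from the ratio of total mean minutes.
- Where the range includes the break-even, state the cost conclusion as conditional on the wage.

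No new data are needed: the access logs already supply both clinician types' minutes. The cost is SAP wording and a little more analysis, and the cost conclusion may have to be stated less firmly.
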